#### Medication and adverse events

**Duration of adverse event:** The interval between the start and end or patient worsened in severity or death dates of the adverse event in days.

**Time to first onset (Interstitial lung disease):** Time between baseline visit and first occurrence of Interstitial lung disease, in weeks, within patients with this adverse event.

**Time to first onset (Stevens-Johnson syndrom):** Time between baseline visit and first occurrence of Stevens-Johnson syndrom, in weeks, within patients with this adverse event.

**Duration of study drug dispensability:** The interval between the dispensed medication date at baseline and the returned medication date at the end of study treatment visit in weeks.

**Drug compliance:** The ratio of used units (tablets) (dispensed at a visit) to number of days between visits. In case the prescribed dose is 50mg, the denominator of this ratio will be multiplied by two.

**Weighted average doses:** the weighted average doses of each patient will be calculated according to the following formula

$$\frac{(150mg \times \text{days on dose } 150mg) + (100mg \times \text{days on dose } 100mg) + (50mg \times \text{days on dose } 50mg)}{\text{total number of days taking medication}}$$

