5.3 Clinical Assessments and Procedures

Testing for EGFR mutation will be performed only at Screening. All of the other clinical and safety assessments will be performed at Screening, Baseline and on Day 1 of every 8th week until PD, death, or unacceptable toxicity, as indicated in the Schedule of Assessments. For all patients who have discontinued study drug treatment and are alive, information on further therapy for NSCLC and survival will be collected.

Tumor Response Criteria

Tumor response will be evaluated according to the RECIST criteria (Eisenhauer et al., 2009) (see Appendix 1).

In this study, tumour response will be measured using computer tomography (CT) or magnetic resonance image (MRI) scans of the chest and upper abdomen, for imaging of liver and adrenal glands. Patients known to have bone metastasis or displaying clinical or laboratory signs (e.g. serum alkaline phosphatase (ALP) > 1.5 ULN) of bone metastasis should have an isotope bone scan at baseline. In cases where there are suspected brain metastases, CT scanning of the brain will be performed.

Post-baseline assessments are to be performed within +/- 5 days for the 8 weekly assessments. If there is suspicion of disease progression based on clinical or laboratory findings, a tumour assessment should be performed as soon as possible, before the next scheduled evaluation.

Consistency of consecutive CT-scans, X-rays or MRIs should be ensured during all assessments for each patient, with the same technique being used for evaluating lesions throughout the treatment period. The use of spiral CT or MRI is required for baseline lesions of < 20 millimetres (mm) and must be documented in medical records and used consistently throughout the study. The use of oral and IV contrast etc. should, as long as it is clinically possible, be kept consistent. Tumor measurements should be made by the same investigator/radiologist for each patient during the study to the extent that this is feasible.

Scheduling of tumour assessments

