6. INVESTIGATIONAL MEDICINAL PRODUCT

6.1 Dose and Schedule of IMP and Comparator(S)

Erlotinib will be administered as single daily oral dose of 150 mg, until disease progression or unacceptable toxicity. No dose escalation of erlotinib is permitted. Dose reduction will be allowed according to protocol (Section 6.1.).

Dose Modifications, Interruptions and Delays

Reduction of dosing for adverse events may take place at any time during the study.

Diarrhoea and skin rash are the major side effects associated with erlotinib. Other known side effects, include dry skin, fatigue, pruritus, nausea, vomiting, anorexia, abdominal pain,

gastrointestinal perforation, dry mouth, dry eye, and headache. Dose reductions can be made according to the system exhibiting the greatest degree of toxicity. All toxicities will be graded according to the NCI CTC-AE version 4.0.

In the event of toxicity (e.g., diarrhoea, rash) that is not controlled by optimal supportive care, or not tolerated due to any reason, regardless of severity, the daily dose of erlotinib will be decreased to 100 mg/day.

Within 2 weeks following a dose reduction, erlotinib related toxicity must improve by at least one NCI-CTC grade and be NCI-CTC Grade 2 or better (any ocular toxicity must improve to NCI-CTC Grade 1), or a further dose reduction to 50 mg/day will be required.

Table 3 - Dose Level Reductions

Starting Dose	First reduction	Second reduction
150 mg/day	100 mg/day	50 mg/day

Patients who cannot tolerate a dose reduction to 50 mg/day will be permanently discontinued from the study.

Dosing may be interrupted for a maximum of 2 weeks if clinically indicated and if the toxicity is not controlled by optimal supportive medication.

Once a patient has had a dose reduction for toxicity, the dose will not be re-escalated except in the case of erlotinib related rash. In the event of a rash, dose can be re-escalated when rash is NCI-CTC Grade 2.

Supportive Care Guidelines

Diarrhoea:

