### **5.3.10.1 Drug dispensing and accountability**

During the treatment period, the number of patients whose study medication was dispensed will be evaluated together with the frequency of patients starting the study with doses of 150mg, 100mg or 50mg, the median (range) duration of study drug dispensability, and the mean (SD)/median (range) number of respective units (tablets) dispensed. Moreover, the percentage of patients who kept the same initial dose until the end of study treatment and who had to change dose will be calculated as well as the mean of the weighted average doses of each patient (the weights being the time a patient was on each dose).

At the end of study treatment, the mean (SD) compliance ratio for each patient will be derived, and the respective percentage of compliant patients assessed. Furthermore, a patient will be deemed compliant if the compliance ratio is at least 80%.

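### The compliance ratio counts protocol-permitted hold days as missed doses and has no defined value for an interval with a change to 50 mg

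*SAP*

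**What the plan says.** SAP Appendix 3 (Derived Variables, Medication and adverse events) gives drug compliance as "The ratio of used units (tablets) (dispensed at a visit) to number of days between visits". It makes one adjustment: "In case the prescribed dose is 50mg, the denominator of this ratio will be multiplied by two". It has no term for interruption days and does not say which dose governs an interval that contains two.

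SAP 5.3.10.1 says that at the end of study treatment "the mean (SD) compliance ratio for each patient will be derived", and that "a patient will be deemed compliant if the compliance ratio is at least 80" per cent. It does not say how the interval ratios combine into the patient's figure, and it sets no upper limit.

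Protocol 6.1 states: "Dosing may be interrupted for a maximum of 2 weeks if clinically indicated and if the toxicity is not controlled by optimal supportive medication". Its Table 4 also directs holds or interruptions for several graded toxicities, including diarrhoea and rash. On timing of reductions it says: "Reduction of dosing for adverse events may take place at any time during the study". Visits are eight weeks apart: "Post-baseline assessments are to be performed within +/- 5 days for the 8 weekly assessments".

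The compliance result appears in SAP Table 22 and, through SAP 6.12, in the interim analysis.

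**The concern.** A compliance ratio should compare what the patient took with what the patient was told to take. This one compares it with calendar time. A patient told to stop for two weeks, who stops and then restarts as instructed, loses those days from the numerator and keeps them in the denominator. The shortfall looks the same as two weeks of forgotten tablets.

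The doubling for 50 mg works for a whole interval at that dose but not when the dose changes inside one. The programmer must then choose a rule that the SAP does not supply.

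At stake is whether the percentage of compliant patients means what its label says. The error is most likely in patients with toxicity, because toxicity is what triggers holds and reductions. With about 30 patients, each misclassified patient moves the percentage by 1/30, or 3.3 points.

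**Working it through.** **Inputs**

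- Interval: 8 weeks = 56 days, window ±5 days (Protocol 5.3).
- Longest permitted hold: 14 days (Protocol 6.1).
- Tablets per day: strengths are 150, 100 and 25 mg (Protocol 6.3), so 1 per day at 150 or 100 mg and 2 per day at 50 mg.
- Cut-off: 80% (SAP 5.3.10.1).

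The documents give no worked compliance value to reproduce. A check that the rule works in the simple case comes first.

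**1. Constant dose, no hold, perfect intake.** 150 mg: 56/56 = 100%. 100 mg: 56/56 = 100%. 50 mg: 112/(2 × 56) = 100%. The rule is correct here.

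**2. One hold in one interval, perfect intake otherwise.** Ratio = (interval − hold)/interval.

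- 14 days in 56: 42/56 = 75.0%.
- Same hold at the ends of the visit window: 37/51 = 72.5%; 47/61 = 77.0%.
- Crossing point in 56 days: an 11-day hold gives 45/56 = 80.4% (passes); 12 days gives 44/56 = 78.6% (fails).

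**3. Patient level.** One 14-day hold among k equal intervals: (0.75 + (k − 1))/k.

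| Intervals | Patient's figure |
|---|---|
| 1 | 75.0% |
| 2 | 87.5% |
| 3 | 91.7% |
| 7 | 96.4% |

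Seven intervals is an illustration only. It matches the 13.1-month median PFS that Protocol 1.3 cites from another erlotinib study (about 399 days).

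Pooled over D days of treatment, the ratio is (D − 14)/D, which is below 0.80 when D < 14/0.20 = 70 days. For repeated 14-day holds in h of k equal intervals, 1 − 0.25h/k < 0.80 requires h/k > 0.8. Two holds in two intervals give 75%; two in three give 83.3%.

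**4. Early stopping (assumed timing).** Under Table 4, a patient who has not recovered after 14 days of holding is to be discontinued. If the hold starts on day 28 and the end-of-treatment visit is on day 42, full adherence reads 28/42 = 67%.

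**5. Why the combination rule matters.** Take one clean 56-day interval, then a final 28-day interval with a 14-day hold (assumed timing). The unweighted mean is (100% + 50%)/2 = 75%. Pooled, it is (56 + 14)/84 = 83.3%. The SAP allows either, and the label differs.

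**6. Change to 50 mg on day t, perfect intake, one 56-day interval.** Tablets = t + 2(56 − t).

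| Day of change | Tablets | Denominator 112 | Denominator 56 |
|---|---|---|---|
| 7 | 105 | 93.8% | 187.5% |
| 14 | 98 | 87.5% | 175% |
| 28 | 84 | 75.0% | 150% |
| 42 | 70 | 62.5% | 125% |
| 49 | 63 | 56.3% | 112.5% |

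If the interval is split on day 28, the parts are 28/28 and 56/(2 × 28), both 100%. Without doubling, the error can hide poor adherence: true adherence of 54% with a day-28 change reads 0.54 × 84/56 = 81% and passes.

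**7. Denominator of tablets due.** Hold: 42/42 = 100%. Day-28 change: 84/(28 + 56) = 100%.

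**The case against.** The strongest reply is that 75% belongs to an interval, while the 80% cut applies to a patient. A reader might infer that any patient with a two-week hold is labelled non-compliant. The documents do not support that: over two or more equal intervals, a single hold of maximum length still passes. Maximum-length holds in nearly every interval would be unusual, since most Table 4 holds restart at a reduced dose and only two reduction levels exist. The documents give no frequency for either situation. This stands, and it limits the size of the problem.

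On 50 mg, the patient needs a different tablet strength. If the contact at which it is dispensed counts as a visit, the interval splits there and the anomaly disappears. That is a fair reading, but the SAP does not state it. The 75% and 150% figures also need a change at the midpoint.

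A reader might also infer that the ratio measures toxicity instead of adherence. That goes too far. A reduction to 100 mg leaves the ratio unchanged, constant 50 mg is handled correctly, and dose reductions and interruptions are reported separately in SAP Tables 22 and 28.

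Finally, compliance is descriptive and the trial tests no hypothesis. That is true. It makes the point modest, but the row would still be wrong for the patients affected.

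**Conclusion.** The denominator is wrong for any interval with a directed hold, and undefined for an interval with a change to 50 mg unless the interval is split at the change. This is more than missing detail: for holds, the stated rule applied exactly gives 75% for a fully adherent 56-day interval with a 14-day hold.

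Misclassification of a patient is narrower. Pooled over treatment, a single 14-day hold causes it only when treatment lasts less than about 70 days, as in early stopping for toxicity. Otherwise holds must recur; at 14 days each in equal 56-day intervals, that means more than four-fifths of them. The number of such patients cannot be estimated from the documents.

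The effect is limited to the compliance rows of SAP Table 22 and the interim compliance summary. Because dosing deviations count as major in the protocol-deviation table, a reader might infer that the 80% rule removes patients from the per-protocol population and so alters that ORR analysis. No text makes that link, and the primary ORR analysis is on the intent-to-treat population.

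The figures assume perfect intake on prescribed days and, except where noted, 56-day intervals.

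**What to change.** In SAP Appendix 3, define compliance as tablets used divided by tablets due. Tablets due is summed over days when dosing was prescribed: 1 per day at 150 or 100 mg, 2 per day at 50 mg, and 0 on investigator-directed hold days. Compute it once per patient over the whole treatment period, and say so in SAP 5.3.10.1. This settles how intervals combine and removes the mixed-dose problem.

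First confirm that hold and dose-change dates are captured in the dosing or adverse-event action records. This cannot be taken for granted. The days-on-dose terms in the weighted average dose do not separate directed holds from skipped doses, and SAP 5.3.9.2 states that even the first-dose date is not in the CRF. If the dates are not available, label the figure as tablets taken relative to calendar days and do not class patients as non-compliant from it.

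An upper limit for overuse is optional and for the sponsor to choose.

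The cost is one rewritten derivation, a check of the CRF, and a little more programming, provided the dates exist.

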#### Study populations

**ITT:** A dichotomous variable (yes/no) will be calculated. Patients who are enrolled to the treatment phase of the study (baseline visit) will be classified in “yes”. Otherwise patients will be classified in “no”.

**PP:** A dichotomous variable (yes/no) will be calculated. Patients who are enrolled to the treatment phase of the study (baseline visit) and without major protocol violations will be classified in “yes”. Otherwise patients will be classified in “no”.

**Safety:** A dichotomous variable (yes/no) will be calculated. Patients who received at least one dose of study medication will be classified in “yes”. Otherwise patients will be classified in “no”.

---

## Appendix 4: Handling incomplete dates

### **Birth dates**

If only the year is known, the complete date will be assumed to be July 1st of the given year. If both month and year are known, the complete date will be assumed to be the 15th of the given month.

### **Death dates**

If both month and year are known, the complete date will be assumed to be the 1st of the given month.

If only the year is known, the complete date will be:

- the date of last visit or last contact with the patient, if the year of death is equal to the year of last contact
- the 1st day of the year, if the year of death is higher than the year of last contact.

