5.6 Survival Follow-up Phase

After the final visit has been completed the patient should be followed every 6 months (\pm 15 days), or as appropriate evaluated by the investigator, for collection of subsequent therapies and survival status.

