### **5.3.9.2 Secondary Efficacy Endpoints**

The secondary efficacy variables include:

- Progression-free survival (PFS), defined as the time from baseline visit to the date of first occurrence of disease progression or death for any cause while the patient was under study or during the prolonged follow-up period. PFS will be summarized as median time and will be estimated using the Kaplan-Meier method. Ninety five percent (95%) confidence interval will be estimated for median time to PFS.
  
- Overall survival (OS), defined as the time from the first dose of erlotinib to the date of death due to any cause while the patient was under study or during the prolonged follow-up period. Overall survival variable will be summarized as median time to OS and will be estimated using the Kaplan-Meier method. 95% confidence interval will be estimated for median time to OS. The date of first dose is not captured in the study CRF. Therefore, for this endpoint it will be assumed that the patient will take the first dose at the day of the baseline visit.
  
- Epidermal growth factor receptor (EGFR) mutation frequency. The presence of EGFR mutation (exon 19 deletion and/or exon 21 substitution L858R) in the study population will be presented as the relative frequency of those mutations among the total screened patients. A 95% confidence interval will be estimated for this value using binomial distribution.
  
- Response duration, defined as the time of initial response (CR/PR whichever is first recorded) until documented tumor progression. Response duration will be summarized as median time and will be estimated using the Kaplan-Meier method. Ninety five percent (95%) confidence interval will be estimated for median time to response duration.

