## **5.4 MISSING DATA**

Incomplete dates will be handled as stated in Appendix 4. All other missing values will be individually omitted from the analyses.

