### Treatment period

**Response duration:** It will be measured from the time of initial response (CR/PR whichever is first recorded) until documented tumor progression (in weeks).

**Best overall response:** a categorical variable will be obtained, defined as the best response across all time points, according to RECIST 1.1, until end of study treatment. The following criteria will be considered:

Complete response – Patients who presented at least one complete response;

Partial response – Patients who not presented a complete response and presented at least one partial response;

Stable disease – Patients who not presented response (complete or partial) and presented at least one stable disease;

Progression disease – Patients who not presented response or stable disease and presented progression disease;

Inevaluable – All assessments are inevaluable.

**Objective response:** A dichotomous variable (yes/no) will be calculated. Patients who presented complete response or partial response as the best overall response will be classified in “yes”. Otherwise patients will be classified in “no”.

**Event PFS:** A dichotomous variable (yes/no) will be calculated. Patients who presented progression disease or death for any cause will be classified in “yes”. Otherwise patients will be classified in “no”.

**Time PFS:** Time between baseline visit and date of first occurrence of disease progression or death for any cause (in weeks) while the patient was under study or during the prolonged follow-up period. In patients where disease progression or death from any cause was not observed, the time will be censored at the date of last visit or last contact with the patient.

**Time overall survival:** The time from the first dose of erlotinib (assumed to be baseline visit) to the date of death due to any cause (in weeks). For patients alive at the end of the follow-up period, the time was censored at the date of last visit or last contact with the patient.

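### Deaths with a known month but no day are set to the 1st of the month, so an imputed death can precede the date the patient was last known alive

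*SAP*

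**What the plan says.** SAP 5.4 states: "Incomplete dates will be handled as stated in Appendix 4". For deaths, Appendix 4 has three cases.

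- **Month and year known:** "If both month and year are known, the complete date will be assumed to be the 1st of the given month". No condition is attached.
- **Only the year known, same year as last contact:** "the date of last visit or last contact with the patient, if the year of death is equal to the year of last contact".
- **Only the year known, "if the year of death is higher than the year of last contact":** 1 January of the year of death, which is necessarily after last contact.

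The imputed date feeds two endpoints. OS runs from first dose, taken as the baseline visit, to death. For patients still alive, Appendix 3 says "the time was censored at the date of last visit or last contact with the patient". PFS is defined in SAP 5.3.9.2 as the "time from baseline visit to the date of first occurrence of disease progression or death for any cause". Neither definition, nor the derived variables in Appendix 3, compares an imputed death with other recorded dates.

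On treatment, visits and scans are 8-weekly, with unscheduled scans if progression is suspected (Protocol 5.3). Survival follow-up is 6-monthly, "or as appropriate evaluated by the investigator, for collection of subsequent therapies and survival status" (Protocol 5.6).

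**The concern.** Placing a death on the 1st of the month may be a deliberate early convention, and that choice is not the issue. The issue is that the rule can contradict recorded data. If the patient was seen, contacted or scanned after the 1st of the month of death, the imputed death comes before that date.

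This has three consequences. A more complete death date can give a worse imputed date than a less complete one. A patient known to have died can receive a shorter OS than the same patient censored alive. A progression documented by scan can be displaced by a death imputed to precede it, which changes both the PFS time and the event type. A programmer who meets such a case must either leave it in the tables or make up a rule after seeing the data.

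**Working it through.** The plan gives no figure for this point, so there is nothing to reproduce. The rule is applied first to one patient and then to assumed contact patterns.

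**1. One patient.** Baseline 8 January 2013; unscheduled scan showing progression on 20 March 2013, also the last contact; death later in March.

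| What is recorded | Date used | Time from baseline |
|---|---|---|
| Alive at last contact (censored) | 20 March | 71 days = 10.1 weeks |
| Death, year only (2013) | 20 March | 71 days = 10.1 weeks |
| Death, March 2013 | 1 March | 52 days = 7.4 weeks |

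Knowing the month moves OS back by 19 days, to a date on which the patient was demonstrably alive. PFS also becomes 7.4 weeks with death as the event, instead of 10.1 weeks with progression. With a baseline of 10 March and a death in March, the time is 1 March minus 10 March = -9 days.

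**2. How often.** Assumptions: the death day is uniform over the 365 days of 2013, and the time since last contact, g, is uniform on 0 to G-1 days. G = 182 represents 6-monthly contact and G = 56 represents 8-weekly contact.

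- A death on day k of the month is imputed k-1 days early. Summed over the year (seven months of 31 days, four of 30, one of 28): 7 x 465 + 4 x 435 + 378 = 5,373 days. The mean is 5,373 / 365 = 14.72 days early, and the maximum is 30.
- The imputed death precedes last contact when g < k-1, which is k-1 of the G possible values. The share is therefore 14.72 / G.
  - G = 182: 14.72 / 182 = 8.1%
  - G = 56: 14.72 / 56 = 26.3%
- Among these conflicts, the imputed death precedes last contact by 10.49 days on average and by at most 30 days.
- With an assumed five month-only deaths: 5 x 0.0809 = 0.40 patients and 5 x 0.2629 = 1.31 patients.

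A separate simulation that excludes contact on the day of death itself gave about 8% and 25%. For an assumed 28-day contact gap it gave 49%.

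**3. Negative times.** With 2,000,000 simulated patients, baseline uniform over one year and exponential OS, the imputed death precedes baseline in 2.8% of month-only deaths (assumed median 12 months) or 1.4% (24 months). Even if all 30 patients died with the day missing, that is 0.83 or 0.42 patients.

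**4. With a last-known-alive floor.** The mean early shift falls by the conflict share times the mean excess:

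- 6-monthly: 14.72 - 0.0809 x 10.49 = 13.87 days
- 8-weekly: 14.72 - 0.2629 x 10.49 = 11.96 days

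The floor removes every conflict with a recorded date on which the patient was alive, but only part of the early shift.

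**The case against.** The strongest reply is that the effect is too small to matter. There is no hypothesis test, OS and PFS are mainly summarised by Kaplan-Meier medians, and the primary endpoint is untouched. In a simulation of 30 patients with five month-only deaths, exponential OS (median 12 or 24 months) and no censoring, adding the floor leaves the median OS unchanged in about 90% of trials with 8-weekly contact and 97% with 6-monthly contact. The mean change is at most about 0.5 days, against a sampling standard deviation of the median of about 95 or 189 days. This stands: the reported medians would rarely move.

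Other points also have force. Missing days of death are more likely in survival follow-up, so 8.1% is probably nearer the truth than 26.3%, although the documents give no rate by phase and Protocol 5.6 allows other intervals. The percentages concern last contact. Displacing a progression also requires a scan in the month of death, and for most deaths in follow-up the progression will already lie in an earlier month. The negative-time figures are probably upper bounds, because they assume a constant hazard from day 0 whereas Protocol 4.2 requires a life expectancy of at least 12 weeks. The fix also leaves most of the early shift in place.

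None of this makes the rule correct. Followed exactly, it can produce a death before a documented contact, and the year-only rule already avoids that outcome.

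**Conclusion.** The concern holds. The month-known rule in SAP Appendix 4 can produce impossible date orderings, and nothing else in the SAP or protocol prevents them. The plan protects the less complete death date and leaves the more complete one unprotected.

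The expected effect is small: 0.4 to 1.3 patients per five month-only deaths, wrong by 10.5 days on average. This rests on the uniform-timing assumptions, 6-monthly or 8-weekly contact, and an assumed number of partial dates that is probably small in practice. OS is affected directly. PFS is affected when death is the first event or when the imputed death moves ahead of a progression scan in the same month. ORR does not use death dates, and response duration is defined to documented progression. No conclusion of the trial is likely to change, but the rule should be corrected because it is wrong as written and the correction is almost free.

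**What to change.** Add one sentence to SAP Appendix 4, Death dates:

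> The imputed death date is the later of the date given by the rule above and the last date on which the patient is known to have been alive (baseline, any visit, any scan including a progression scan, or any contact confirming that the patient was alive).

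The final words matter because Protocol 4.6 allows contact with a relative; a call in which a relative reports a death in an earlier month must not move the death to the date of the call. Apply the floor before OS and PFS are derived.

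The cost is this sentence and one maximum in the derivation. The last-visit or last-contact date is already needed for censoring, and progression dates are already needed for PFS and response duration. The case report form is not among the documents, so the availability of other scan dates should be confirmed. The remaining early shift of about 12 to 14 days for month-only deaths comes from choosing the 1st of the month and is not removed by this change.
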